We will measure HED with a question on how often the respondent drank 5 or more drinks on a single occasion (considering a 1-month period). The options were never, once, twice, 3 to 5 times, 6 to 9 times and 10 or more. We will convert this information into a continuous variable. We will convert the options 3-5 and 6-9 times to their arithmetic midpoint (4 and 7.5, respectively). We will convert the 10 or more option into the lower boundary (i.e., 10). This data is available for waves 0, 1, 4, 5 and 6.

We will measure the number of daily cigarettes smoked per day with a question on how many cigarettes has the participant smoked on average during the past week. We will convert this information into a continuous variable. This data is available for all waves.

Procedures

We collected the data using an online survey sent by email to all eligible participants. Data were collected from July 27 to August 13 (wave 0 and 1), August 15 to August 25 (wave 2), September 7 to September 22 (wave 3), October 5 to October 16 (wave 4), November 9 to November 20 (wave 5), December 9 to December 21 (wave 6) and April 5 to April 23 (wave 7). In all waves, we used an online survey tool (QuestionPro) which creates a database automatically. We did not allow participants to leave questions blank, but participants could stop answering at any moment. We used the following protocol to remind participants to answer the questionnaire: After sending the survey, we sent a reminder every three days: twice via email, then to those who had provided a mobile phone number, we sent the survey

two more times via text messaging. No incentive was provided in exchange for their participation in any of the study waves. The first round of data collection included questions regarding the period before the COVID-19 pandemic (wave 0) and during the pandemic (wave 1).

Sample size calculation

Prior to the beginning of the study, we calculated a sample size of 1046 participants to detect a small effect size (0.2), with a statistical power of 0.95, alpha of 0.05 and a factor of 2 to take into account the impact of attrition.

Ethical approval

The Scientific Ethics Committee from the Universidad de la Frontera and Universidad Católica del Norte approved the study in accordance with Law 20.120 (2006). We obtained electronic written consent from all participants.

Statistical analysis

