We will exploit the variation in lockdown policies in the two regions to measure the effect of lockdown on alcohol use. For this purpose, we will use a difference-in-difference (DiD) design to compare the effect of lockdown in multiple treatment periods. DiD is a quasi-experimental approach that allows using longitudinal data to obtain causal effects in the absence of randomization [33]. DiD is a well-established method in public health research and was first used by John Snow in his seminal study on the transmission of cholera in 1855 [34].

The canonical DiD consists of two time periods and two groups. One computes the difference in the mean outcomes of the treatment and control group after the treatment and subtract the difference that existed before treatment had any effect [35].

$$\delta_{DD} = (\underline{Y}_{posttreat} - \underline{Y}_{pretreat}) - (\underline{Y}_{postcontrol} - \underline{Y}_{precontrol})$$

The key identifying assumption is that, in the absence of treatment, the average outcomes would have followed parallel paths over time [33].

As depicted in Figure 1, our case is more complex, as there are multiple time periods (seven in total) and two groups that are both treated and not-treated in different time periods. For τ periods and a particular time period denoted by t where $t=1,..., \tau$, t_0 represents the baseline measurement captured retrospectively at t_1 . In time periods t_1 , t_2 and t_3 , the Coquimbo group

is exposed to lockdown while the Araucanía group is exposed to less restrictive social distancing policies. At t_4 both groups are exposed to step 2 social distancing policies and at t_5 and t_6 ; this situation reverses, and Araucanía is exposed to lockdown and Coquimbo moves to less restrictive social policies. Treatment intensity *D* has values ranging from 5 (step 1) to 1 (step 5) (see Table S2 for details).

[figure not shown]

Figure 1. Social distancing policies in Coquimbo and Araucanía for the study period

In this setting, we will use a generalized difference-in-difference that allows for multiple treatment periods and several treatment intensities [36, 37]. The regression of a DiD model can be expressed in more general terms as

$$(1) Y_{ist} = \alpha + \delta_{DD} TREAT_{st} + \theta X_{ist} + \beta_i + \gamma_t + e_{ist}$$

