where Y_{ist} is the outcome for an individual s at time t and i is the region (Coquimbo or Araucanía), δ_{DD} is the coefficient of interest of a treatment intensity variable, X_{ist} is a vector of control variables (e.g. age, sex), β_i is a region fixed effect, and γ_t is a set of time fixed effects. The identifying assumption, in this case, relies on a common trend assumption that both treatment groups would develop equally over time under at least one of the treatments. It assumes effect homogeneity conditional on observables X_{ist} .

An alternative to adjustment by control variables would be to use propensity score matching (PSM). Recent analyses Daw and Hartfield (2018) suggest that using PSM could increase bias due to regression to the mean when treatment assignment occurs at the population level. In this context, the difference between treatment groups is stable and unmatched analysis is unbiased. Matching on the preperiod level introduces regression to the mean bias [38]. For this reason, we chose to adjust for control variables and not to use PSM.

There is an ongoing debate about DiD when groups of units receive treatment at different times or different treatment intensities.[39, 40] Researchers are concerned this fixed effect regression provides greater weights to treatments with similar before and after treatment periods and uses treated units as controls.[39] This is unlikely to affect our study, as it has only two treated groups and thus no variation in treatment timing. Nonetheless, we will use the Callaway-Sant'Anna method (CS method) in sensitivity analyses. The method was built to handle staggered treatment adoption designs.[40] To accommodate this, we will divide the analysis into two sections (t_0 versus t_1 , t_2 and t_3) and (t_0 versus t_5 and t_6).

The estimation will be done using linear mixed effects models. These models take into account the correlated nature of the data (repeated measures of the same individuals) and provide mathematically equivalent estimates than fixed effects linear regression. However, an additional advantage of linear mixed effects models is that they allow to vary the number of observations within each participant, handling missing data more efficiently than other analytical approaches [41].

Statistical Software

We will use R (current version 3.6.3) for all analyses. We will use the *lme4* function to run the DiD model and the *did* package for the Callaway-Sant'Anna method.

References

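### The plan says without condition that the mixed model equals fixed-effects regression; with missed waves this fails, and response tied to drinking level and lockdown or region could separate the two estimates.

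*Combined protocol and SAP*

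**What the plan says.** Under Statistical analysis the protocol states: "The estimation will be done using linear mixed effects models". It gives two reasons besides the correlation of repeated measures. The first is that these models "provide mathematically equivalent estimates than fixed effects linear regression", with no condition attached. The second is that "they allow to vary the number of observations within each participant, handling missing data more efficiently than other analytical approaches".

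The second reason presupposes that participants will contribute different numbers of waves. Other sections point the same way. The sample size includes "a factor of 2 to take into account the impact of attrition", and under Procedures "participants could stop answering at any moment".

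The fixed-effects regression being compared is not named. In equation (1), β_i "is a region fixed effect, and γ_t is a set of time fixed effects". The equation also carries the covariate vector X but has no participant term. No planned analysis contains participant fixed effects.

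**The concern.** A random-intercept model and a participant fixed-effects model give the same lockdown coefficient in a complete panel of this design. Once people miss waves, the mixed model also uses differences between people, and the fixed-effects model does not. The plan therefore supports its estimator with a property that its own expected data will not have.

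This matters if the people who answer during lockdown differ in drinking level from those who answer at other times, or if drop-out relates to drinking differently in the two regions. The two models then give different answers to the study's causal question. A reader told that they are equivalent has no reason to look for the difference.

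**Working it through.** **Inputs from the documents.** Seven time periods, t_0 to t_6; lockdown in Coquimbo at t_1 to t_3 and in Araucanía at t_5 and t_6 (Statistical analysis). Effect size 0.2, N = 1046 and an attrition factor of 2 (Sample size calculation). The 0.2 is taken as SD units and the factor of 2 as about half lost or not responding; the plan states neither. The 1046 itself is not at issue here.

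**Inputs not in the documents, so assumed.** Within-person correlation (ICC) 0.3, 0.5 and 0.7; the response mechanism; normal outcomes; a random intercept only; t_0 untreated in both regions. Skewed drinking data were not simulated.

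**Step 1: why balance matters.** A random-intercept fit amounts to regression on y_it − λ_i·ȳ_i, where λ_i = 1 − √[(1 − ρ)/(1 − ρ + T_i·ρ)] and T_i is the number of waves answered. Participant fixed effects correspond to λ = 1. At ρ = 0.5:
- T = 7: λ = 1 − √(0.5/4.0) = 0.65
- T = 2: λ = 1 − √(0.5/1.5) = 0.42

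So the mixed model removes only part of each person's level. In a complete panel this is harmless: the person mean of lockdown exposure is 3/7 for everyone in Coquimbo and 2/7 for everyone in Araucanía, and the region effect absorbs it. Time-fixed covariates do not alter this. A Coquimbo participant who misses t_2 and t_3 has a mean of 1/5 instead of 3/7. Exposure then varies between people within a region, and that variation enters the estimate. Heavy episodic drinking is unmeasured for everyone at waves 2 and 3, so that gap alone does not unbalance the panel.

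**Step 2: the plan's claim with complete data.** In simulation the mixed-model and participant fixed-effects estimates were identical (gap 0 at every ICC). The statement is correct in that case.

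**Step 3: drop-out, about 50% left at t_6, N = 1046.** Mixed minus fixed effects, as % of the 0.2 target:

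| Drop-out | ICC 0.3 | ICC 0.5 | ICC 0.7 |
|---|---|---|---|
| Random: mean gap | 0 | 0 | 0 |
| Random: mean absolute gap in one data set | 2.1 | 1.3 | 0.7 |
| Related to level equally in both regions: mean gap | 0 | 0 | 0 |
| Related to level in one region only (log-odds 0.5 per SD of person effect) | 9.2 | 6.5 | 3.7 |
| Related to level in opposite directions by region | 18.2 | 12.8 | 7.4 |

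**Step 4: one response rule for both regions, in which non-response during lockdown waves rises with usual level.** 20,000 people, 8 runs per scenario, about 50% response at t_2 to t_6, true effect 0. Mixed-model bias in SD, with % of target (bias ÷ 0.2):

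| Odds ratio per SD | ICC 0.3 | ICC 0.5 | ICC 0.7 |
|---|---|---|---|
| 1.5 | −0.030 (15%) | −0.020 (10%) | −0.011 (5.5%) |
| 2.0 | −0.046 (23%) | −0.033 (16.5%) | −0.017 (8.5%) |
| 2.7 | −0.058 (29%) | −0.043 (21.5%) | −0.026 (13%) |

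Fixed-effects bias stayed within 0.003 SD. Monte Carlo error is about 0.001 to 0.003 SD.

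**Step 5: response driven by first-survey answers instead.** The order reverses. The mixed model is near 0 and fixed effects is biased by +0.013 to +0.066 SD over the same grid. At ICC 0.5 the gap is 10%, 16% and 22% of target, almost the same as in step 4.

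**Step 6: what this does to a test.** At N = 1046 and ICC 0.5 the simulated standard error was about 0.027 SD. With bias b and no true effect, the two-sided 5% test rejects with probability Φ(−1.96 + b/SE) + Φ(−1.96 − b/SE).
- b = 0.020: b/SE = 0.74, about 11%
- b = 0.043: b/SE = 1.59, about 36%

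**Step 7: the other reading of fixed effects.** If the comparison is with ordinary least squares on equation (1) as printed, equality again holds with complete data. Random drop-out gives mean absolute gaps of 3.9%, 5.5% and 7.0% of target (ICC 0.3, 0.5, 0.7), and region-differential drop-out gives systematic gaps of about 17% to 72%. The statement needs the complete-data condition on either reading.

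**The case against.** The sentence is a justification. The mixed model is the chosen estimator and no planned result is computed from the equivalence, so correcting the sentence changes no planned number. That stands. It would be wrong to infer that the plan depends on the equivalence or that the team would be stopped from checking.

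A reader might infer that missed waves alone distort the result. Step 3 shows otherwise: random non-response, or non-response tied equally to drinking level, gives no systematic gap and only 1% to 2% in a typical data set. A systematic gap needs dependence on drinking level together with a difference by lockdown status or region. Nothing in the documents shows that this occurred. Nor do they say whether people who skipped a wave were invited to the next.

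A reader might also infer that the planned estimate is the biased one and the within-person estimate is safe. Step 5 rules that out. When response follows first-survey answers, the mixed model is the better of the two, which fits the plan's missing-data rationale.

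Finally, equation (1) has covariates that could absorb some of the selection. They help only modestly: in one run a covariate explaining 40% of person-level variance moved the bias from −0.039 to −0.034 SD.

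**Conclusion.** The unconditional equivalence statement is wrong for the data the plan expects. The practical consequence is conditional. Under selection linked to both drinking level and lockdown or region, the two estimates differ by about 0.01 to 0.06 SD, roughly 5% to 30% of the 0.2 target. The range rests on assumed ICCs of 0.3 to 0.7 and odds ratios of 1.5 to 2.7 per SD. A higher ICC shrinks the gap: at 0.8 the step 4 scenario gives 4% to 8%. No single percentage can be derived from the documents.

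The documents do not support the stronger conclusion that the planned estimate is biased. A comparison of the two models can reveal selective response but cannot say which estimate is right. The change is worth making because it is cheap and the plan now has no such check: the Callaway-Sant'Anna analysis is offered for treatment timing, not for selective response.

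**What to change.** 1. Restrict the equivalence sentence to complete data, and say whether the fixed-effects model meant has participant effects or only the region and time effects of equation (1).
2. For each primary outcome, pre-specify a sensitivity model with participant fixed effects, reported beside the mixed-model estimate. An alternative is to add each person's means of TREAT and of the wave indicators, taken over the waves answered, to the mixed model.
3. State in advance that a material difference will be read as a sign of selective response that limits the causal conclusion, and not as proof that either estimate is correct.

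The cost is one extra model per outcome on data already collected, plus a few sentences. Time-fixed covariates drop out of the participant fixed-effects model. In simulation at N = 1046 its standard error was about 1% larger than the mixed model's.

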Step 2	Yes	Yes, only Saturdays, Sundays and bank holidays	Remote education for preschool, elementary and higher schools	Open at 25% of their maximum capacity, maximum time two hours, only in open spaces	Sports activities for maximum 10 people in open spaces. Gyms closed	Public events allowed for a maximum of 10 people in a closed space and 20 people in an open space.	Closed	Customer service restricted to no more than 1 person per 10 square meters	Passenger cruises forbidden. All buses must have a list of passengers for travelling times longer than 2 hours. Forbids travel to second residence. 1	Allowed	Lockdown for residents in elderly care. Closure of day centers for older adults and meetings of "Clubes de Adultos Mayores"

Step 3	Yes	No	Allowed after permission from Regional Secretary of Education	Open at 25% of their maximum capacity, maximum time two hours, only in open spaces	Sports activities for maximum 25 people in open spaces and 5 people in closed spaces, including gyms	"Oficios, ritos, seminarios and ceremonias" allowed for a maximum of 25 people in a closed space and 50 people in an open space.	Closed	Customer service restricted to no more than 1 person per 10 square meters	Allows travel to second place of residence	Allowed	Lockdown for residents in elderly care. Closure of day centers for older adults and meetings of "Clubes de Adultos Mayores"
Step 4	Yes	No	Allowed after permission from Regional Secretary of Education	Open at 50% of their maximum capacity	Sports activities for maximum 50 people in open spaces and 10 people in closed spaces, including gyms	"Oficios, ritos, seminarios and ceremonias" allowed for a maximum of 50 people in a closed space and 100 people in an open space.			Allows travel to second place of residence	Allowed	Lockdown for residents in elderly care. Closure of day centers for older adults and meetings of "Clubes de Adultos Mayores"
Step 5	Yes	No	Allowed after permission from Regional Secretary of Education	Open at 75% of maximum capacity	Sports activities for maximum 100 people in open spaces and 20 people in closed spaces, including gyms	"Oficios, ritos, seminarios and ceremonias" allowed for a maximum of 100 people in a closed space and 200 people in an open space.	Open at 75% of maximum capacity		Allows travel to second place of residence	Allowed	Visits to elderly care centers are allowed. Day centers for older adults open

^{1.} Except people older than 65 years old and with chronic conditions. They are allowed to move but must remain in quarantine. Data based on Resolución Exenta 591 from the Chilean Ministry of Health, July 23, 2020

Table S2. Mobility permits during step 1 (lockdown) in Chile during the study period

Permit	Duration
Appointment in a health care centre	3 hours
Shopping for essential goods (food, medications, etc)	3 hours
Going out for a person with autistic spectrum disorder or any other cognitive disability	2 hours, no weekly limit
Walking dogs and other pets, two blocks around the place of residence	30 minutes
Payment of household expenses or collecting pensions or State subsidies	3 hours
Attending funerals of direct relatives	5 hours ¹
Collecting textbooks, school food or technological devices for school purposes	5 hours
Attending a court appointment	No limit
Take food or other essential products to older adults	2 hours
Take food or other essential products to prison inmates	3 hours
Transport children or adolescents between parents or caretakers' residences	2 hours
Visits to people with disabilities that are hospitalized	3 hours
Weddings or civil unions, including a maximum of 5 companions	4 hours
Donate blood	4 hours
Taking care of older adults and people with disabilities	No limit
Other important and urgent matters authorized in person by the Chilean Police Force	Depend

^{1.} If the funeral is in the same region, 24 hours if it's in a different region than the one of residence
